### **8.4 Study Withdrawal, Removal, and Replacement of Patients**

If a patient discontinues study treatment and is withdrawn from the study for any reason, the study site must immediately notify the medical monitor. The date and the reason for study discontinuation must be recorded on the electronic case report form (eCRF). Patients who complete or discontinue early from the study will be asked to return to the study site within 7 days of the last administration of study drug to complete the safety follow-up assessments as indicated in the Schedule of Assessments ([Table 1](#)).

Patients who want to discontinue early from the study (i.e., at the next visit), or who make a decision to withdraw during a scheduled visit, and who remain on study drug should complete

the rating scale/assessments indicated for that visit (Visit 2 or Visit 3) as well as the safety follow-up assessments according to the Schedule of Assessments ([Table 1](#)).

In the event that a patient discontinues prematurely from the study because of a TEAE or serious TEAE, the TEAE or serious TEAE will be followed until it resolves (returns to normal or baseline values) or stabilizes, or until it is judged by the Investigator to no longer be clinically significant.

Once a patient is withdrawn from the study, the patient may not re-enter the study. Care of the patient will return to their usual doctor.

A patient may voluntarily withdraw or be withdrawn from the study at any time for reasons including, but not limited to, the following:

- Unacceptable toxicity or AE.
- Clinically significant abnormal lab values:
  - Alanine aminotransferase (ALT) or aspartate aminotransferase (AST)  $\geq 8x$  upper limit of normal (ULN);
  - ALT or AST  $\geq 3x$  ULN and total bilirubin  $\geq 2x$  ULN at the same visit;
  - ALT or AST  $\geq 3x$  ULN with the appearance of symptoms indicating hepatitis (e.g., worsening fatigue, nausea, vomiting, right upper quadrant pain or tenderness, fever, rash, or eosinophilia).
- QT syndrome, Fridericia's formula corrected QT (QTcF) interval  $\geq 470$  ms (for male subjects) or  $\geq 480$  ms (for female subjects), or torsades de pointes. Abnormal results for ECGs should be confirmed with repeat ECG recordings to ensure reproducibility of the abnormality before withdrawing the subject from the study.
- A positive urinary drug screen at any visit.
- Patient withdrawal of consent: at any time, a patient's participation in the study may be terminated at his/her request or on the basis of the Investigator's clinical judgment. The reason for patient withdrawal will be noted on the eCRF.
- Intercurrent illness: a condition, injury, or disease unrelated to the primary diagnosis that became apparent during treatment and necessitated the patient's termination from the study.
- General or specific changes in the patient's condition that renders him/her ineligible for further treatment according to the inclusion/exclusion criteria.
- Patient fails to adhere to the protocol requirements (e.g., drug noncompliance, failure to return for defined number of visits).
- Lost to follow-up: the patient stopped coming for visits, and study personnel were unable to contact the patient.

- Pregnancy, as indicated in [Section 12.7.6](#).

Additionally, the Sponsor may stop the study at any time for safety, regulatory, legal, or other reasons aligned with Good Clinical Practice (GCP). This study may be terminated at the discretion of the Sponsor or any regulatory agency. An Investigator may elect to discontinue or stop the study at his or her study site for any reason, including safety or low enrollment.

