### **5.2.2 Clinical Studies**

The SUVN-G3031 Phase 1 program included 72 healthy volunteers and provided preliminary clinical safety and pharmacokinetic (PK) data. SUVN-G3031 was well tolerated in both single-dose (up to 20 mg oral [PO]) and multiple-dose administrations (up to 6 mg PO for 14 days). There were no deaths, serious adverse events (SAEs), or treatment-emergent adverse events (TEAEs) leading to discontinuation from the Phase 1 program. The most frequently reported TEAE preferred terms were dyssomnia (33.3%) followed by abnormal dreams (27.8%), and TEAEs that occurred most frequently were in the System Organ Class, Psychiatric Disorders.

A maximum tolerated single dose (20 mg PO) and maximally well tolerated multiple doses of 6 mg/day PO for 14 days were established using a sequential dose-escalation paradigm. Specifically, no significant changes in safety parameters including laboratory results, physical examinations, vital signs, fluid balance, suicidal ideation, and electrocardiogram (ECG) parameters were noted. Pharmacokinetic data suggest dose proportionality across a range from 0.1 mg to 20 mg after single administration of SUVN-G3031 PO, with the main terminal half-life of approximately 23 to 34 hours across dosages evaluated. Multiple oral administration exhibited dose-proportional increases in exposures across 1 mg to 6 mg dose range with steady state achieved in approximately 5 days. Approximately 55% to 60% of the administered dose was excreted via the urinary route. Food, gender, and age had no appreciable effect on the PK profile of SUVN-G3031.

SUVN-G3031 may be used adjunctively with a variety of compounds affecting EDS or cataplexy in patients with narcolepsy as outlined in the Investigator's Brochure. However, SUVN-G3031 is being evaluated as a monotherapy in the current protocol and all adjunctively used compounds affecting EDS or cataplexy in patients with narcolepsy are prohibited.

Further information on clinical studies can be found in the Investigator's Brochure.

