## 12.7 Adverse Events

### 12.7.1 Adverse Events

An AE is any symptom, physical sign, syndrome, or disease that either emerges after the patient signs the ICF or, if present at Screening, worsens after signing the ICF, regardless of the suspected cause of the event. All medical and psychiatric conditions (except those related to the indication under study) present at Screening will be documented in the medical history eCRF. Changes in these conditions and new symptoms, physical signs, syndromes, or diseases should be noted on the AE eCRF during the rest of the study. Clinically significant laboratory abnormalities should also be recorded as AEs. Surgical procedures that were planned before the patient enrolled in the study are not considered AEs if the conditions were known before study inclusion; the medical condition should be reported in the patient's medical history.

Patients will be instructed to report AEs at each study visit. All AEs are to be followed up until resolution or a stable clinical endpoint is reached.

Each AE is to be documented on the eCRF with reference to date of onset, duration, frequency, severity, relationship to study drug, action taken with study drug, treatment of event, and outcome. Furthermore, each AE is to be classified as being serious or nonserious. Changes in AEs and resolution dates are to be documented on the eCRF.

For the purposes of this study, the period of observation for collection of AEs extends from the time the patient gives informed consent until the follow-up visit. Follow-up of the AE, even after the date of therapy discontinuation, is required if the AE persists until the event resolves or stabilizes at a level acceptable to the Investigator.

When changes in the intensity of an AE occur more frequently than once a day, the maximum intensity for the event should be noted. If the intensity category changes over a number of days, then those changes should be recorded separately (with distinct onset dates).

The severity of AEs will be graded according to [Table 3](#).

Specific guidelines for classifying AEs by intensity and relationship to study drug are given in [Table 3](#) and [Table 4](#).

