#### **12.7.4 Serious Adverse Event Reporting**

An SAE occurring from the time informed consent is obtained, during the study, or within 14 days of stopping the treatment must be reported to the [REDACTED] Safety and Pharmacovigilance group and will be communicated to the Sponsor. Any such SAE because of any cause, whether or not related to the study drug, must be reported within 24 hours of occurrence or when the Investigator becomes aware of the event. Notification can be made using the dedicated fax line or email for the [REDACTED] pharmacovigilance group:

[REDACTED]  
[REDACTED]  
[REDACTED]

If the Investigator contacts the [REDACTED] pharmacovigilance group by telephone, then a written report must follow within 24 hours and is to include a full description of the event and sequelae in the format detailed in the SAE reporting form.

The event must also be recorded on the standard AE eCRF. Preliminary reports of SAEs must be followed up by detailed descriptions later on, including clear and anonymized photocopies of hospital case reports, consultant reports, autopsy reports, and other documents when requested and applicable. Serious AE reports must be made whether or not the Investigator considers the event to be related to the investigational drug.

Appropriate remedial measures should be taken to treat the SAE, and the response should be recorded. Clinical, laboratory, and diagnostic measures should be employed as needed in order to determine the etiology of the problem. The Investigator must report all additional follow-up evaluations to the [REDACTED] Safety and Pharmacovigilance group within 24 hours of becoming aware of the additional information or as soon as is practicable. All SAEs will be followed up until the Investigator and Sponsor agree the event is satisfactorily resolved.

Any SAE that is not resolved by the end of the study or upon discontinuation of the patient's participation in the study is to be followed up until it either resolves, stabilizes, returns to baseline values (if a baseline value is available), or is shown to not be attributable to the study drug or procedures.

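### Protocol 8.4 sets no earliest day for an early discontinuer's safety follow-up, so active collection of new non-serious adverse events can end with drug still on board

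*Protocol*

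**What the plan says.** **Timing of the visit.** Protocol 8.4 gives one rule for completers and early discontinuers: "Patients who complete or discontinue early from the study will be asked to return to the study site within 7 days". The limit is counted from the last dose: "within 7 days of the last administration of study drug to complete the safety follow-up assessments". No minimum interval appears there or elsewhere. A second paragraph in 8.4 covers patients who withdraw at Visit 2 or Visit 3 while still on drug. They do that visit's assessments "as well as the safety follow-up assessments according to the Schedule of Assessments", and the time between the two sets is not stated. Protocol 10.2.1 has patients dosed on the morning of those visits.

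**End of collection.** Under Protocol 12.7.1, "the period of observation for collection of AEs extends from the time the patient gives informed consent until the follow-up visit". Serious events have a longer window under 12.7.4: "An SAE occurring from the time informed consent is obtained, during the study, or within 14 days of stopping the treatment must be reported". Events already recorded are protected. For a patient who stops because of an event, 8.4 says "the TEAE or serious TEAE will be followed until it resolves (returns to normal or baseline values) or stabilizes", and 12.7.1 requires follow-up of all recorded events.

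**Completers.** Protocol 7.1.3 and Table 1 put the safety follow-up at Day 21 ± 1. Visit 3 is at Day 14 ± 1, and dosing lasts 14 days (9.2).

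**Pharmacokinetics.** Protocol 5.2.2 reports a "main terminal half-life of approximately 23 to 34 hours across dosages evaluated" in healthy volunteers, with steady state in about 5 days.

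**The concern.** Read together, 8.4 and 12.7.1 let the length of post-treatment observation depend on how soon the patient comes back. A completer is observed for about a week after the last dose. A patient who stops on Day 5 and returns on Day 6 has satisfied 8.4, and active collection of new events then stops.

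What could be lost is new, non-serious events that start after an early visit. These include non-serious forms of the two events of special interest in Protocol 12.7.2 (unpleasant or vivid dreams, and trouble falling or staying asleep). SAP 10.3 counts any event that starts or worsens from the first dose as treatment-emergent and sets no upper limit, so such events would enter the incidence tables if they were collected. The patients concerned include those withdrawn for toxicity, liver enzymes or QTcF.

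A smaller inconsistency affects completers: the 7-day cap in 8.4 excludes some visit days that Table 1 allows.

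**Working it through.** **Inputs.** Half-life 23 to 34 h and steady state at about 5 days (Protocol 5.2.2). Follow-up visit 0 to 7 days after the last dose, with no lower bound (8.4). Serious-event window 14 days (12.7.4). Visit 3 at Day 14 ± 1 and follow-up at Day 21 ± 1 (Table 1). Dropout 10%, with 114 patients planned (Protocol 14.1) and 171 after re-estimation (SAP 3.6). Allocation 1:1:1 (9.3.1).

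**Step 1: the plan's own figure.** The fraction of steady state reached at time t is 1 − 2^(−t/half-life). At 120 h it is 1 − 2^(−120/23) = 97% and 1 − 2^(−120/34) = 91%. The statement of about 5 days is reproduced, so the half-life range is a fair basis for what follows.

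**Step 2: drug remaining d days after the last dose.** Residual = 2^(−24d/half-life).

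| Days after last dose | Half-life 23 h | Half-life 34 h |
|---|---|---|
| 1 | 49% | 61% |
| 2 | 24% | 38% |
| 3 | 11% | 23% |
| 4 | 5.5% | 14% |
| 5 | 2.7% | 8.7% |
| 7 | 0.6% | 3.3% |
| 9 | 0.15% | 1.2% |

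Day 5 is the first whole day below 10% at both ends of the range. The documents define no washout for the study drug, so the 10% mark is a working choice. Five half-lives would be 5 × 23/24 = 4.8 days to 5 × 34/24 = 7.1 days. Visits at 1 to 3 days are early on either criterion.

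**Step 3: serious-event window after the visit.** A visit at 0 to 3 days leaves 14 − 3 = 11 to 14 − 0 = 14 days that rest on unprompted reporting. Over the whole permitted range of 0 to 7 days, the remainder is 7 to 14 days.

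**Step 4: completers.** The interval is the follow-up day minus the last-dose day.

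- Last dose on Day 14: 20 − 14 = 6 to 22 − 14 = 8 days, nominally 21 − 14 = 7.
- Last dose on the day of Visit 3, at the window extremes: 20 − 15 = 5 to 22 − 13 = 9 days.

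The nominal schedule meets the 7-day cap exactly. Only the 8- and 9-day cases breach it. Completers are seen at 5 days or later in every case.

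**Step 5: how many patients.** 10% of 114 = 11.4 and 10% of 171 = 17.1. Two thirds are on active drug if dropout is equal across arms: 7.6 and 11.4. The documents do not say what share return at all. If 25% to 75% do (assumed), that is 1.9 to 5.7, or 2.9 to 8.6, patients on active drug, before asking how many come in the first few days.

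**The case against.** The strongest reply has four parts.

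1. **No off-drug reading is promised.** A reader might infer that follow-up ECG, laboratory and C-SSRS values taken early defeat the purpose of the visit because they do not show the off-drug state. The documents do not support that. Protocol 7.2.2.3 disclaims any attempt to evaluate discontinuation effects, no objective or endpoint asks for an off-drug value, and the C-SSRS at follow-up covers an interval. This part stands, and the point is therefore limited to completeness of event collection.

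2. **A prompt visit is desirable.** After withdrawal for toxicity, ALT/AST elevation or QTcF prolongation, an early check is good care. Moving every follow-up visit to about a week after the last dose could leave a patient who stops at home with no required contact before then. This stands, and the fix keeps the prompt visit.

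3. **The main safety routes are covered.** Serious events remain reportable for 14 days, recorded events are followed up, and the investigator may arrange unscheduled assessments (10.2). This stands for serious and recorded events. It does not reach new non-serious events, because unscheduled assessments are discretionary and no contact is planned after the visit.

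4. **Distortion of the summary tables is not shown.** A reader might infer that early values are pooled with completers' values, since SAP 6.4 applies no windows. That depends on how the visit is entered. SAP 6.1 leaves unscheduled assessments out of the summaries by default, and the data-entry rules are not in the documents.

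A same-day visit is not instructed either: 8.4 asks patients to return, and Table 1 has a separate follow-up column. The plan simply sets no minimum.

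**Conclusion.** The point holds as a minor gap in safety follow-up. For an early discontinuer, active collection of new non-serious adverse events can end 0 to 3 days after the last dose, when 49% to 61% (day 1) to 11% to 23% (day 3) of the drug remains. At the planned dropout, about 11 of 114 or 17 of 171 patients stop early, roughly 8 or 11 of them on active drug. Only those seen early are affected, and some cannot be reached at all. The completer mismatch of 1 to 2 days at the window extremes is tidying.

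The conclusion rests on these assumptions:

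- The healthy-volunteer half-life holds in patients.
- The 10% dropout is a planning assumption and not a maximum.
- Dropout is equal across arms.
- The follow-up visit in 12.7.1 is the patient's own visit under 8.4.

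The consent form is not available, so any instruction to patients about reporting late events cannot be seen. It would be wrong to conclude that serious events go uncollected or that the efficacy result is at risk: the primary endpoint, alpha, power and sample size are not touched.

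**What to change.** **Protocol 8.4, early discontinuers.** Keep the return within 7 days of the last dose. Add that, if this visit falls less than 5 days after the last dose, the site makes a telephone adverse event check 7 ± 2 days after the last dose, or arranges a visit if clinically indicated. The 7 ± 2 days matches the 5 to 9 days that completers already have.

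**Protocol 8.4, completers.** Replace the 7-day cap with a reference to the Day 21 ± 1 visit.

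**Protocol 12.7.1.** State that adverse event collection runs to that later contact where one is made, and that serious-event collection runs to 14 days after the last dose, in line with 12.7.4.

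**Cost.** Some protocol wording and one call per early discontinuer seen before day 5, in all arms because the study is blinded. At the planned dropout that is at most about 11 or 17 calls in total. The completer schedule, the nominal 28 + 21 = 49-day maximum and the sample size do not change. SAP 3.6 shows that the interim re-estimation has been done, so only patients still to finish would benefit.

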## 9 TREATMENTS

### 9.1 Details of Study Treatments

The study treatments to be used in this study are:

- 2 mg SUVN-G3031
- 4 mg SUVN-G3031
- Placebo

All study treatment supplies to be used in this study will be provided by the Sponsor.

Study treatment is provided in high density polyethylene (HDPE) bottles containing 10 tablets. Each bottle will contain the patient identification number, the name and address of the Sponsor, and any other information required by local regulations. Study treatment supplies should be stored in accordance with United States Pharmacopeia (USP) Controlled Room Temperature (20–25°C [68–77°F] with excursions permitted between 15 and 30°C [59–86°F]). Further information is provided in the Pharmacy Manual.

### 9.2 Dosage Schedule

Patients should take 1 tablet per day in the morning, as soon as they wake up, with approximately 250 mL water. Dosing may occur with or without food. Patients will be dosed for 14 days.

If a patient forgets to take their morning dose and remembers before 1:00 PM, then they should take it as soon as they remember. If a patient forgets to take their morning dose and remembers after 1:00 PM, then they should skip the day's dose and take the next scheduled dose the next morning. If the patient has missed more than 1 dose, then they should only take the most recent forgotten dose.

### 9.3 Measures to Minimize Bias: Study Treatment Assignment and Blinding

#### 9.3.1 Method of Study Treatment Assignment

Patients will be randomized to the 3 study treatments in a 1:1:1 ratio. This randomization will be stratified by at least 30% each based on whether they have narcolepsy with or without cataplexy (Na-1 or Na-2), respectively.

Patients will be randomized using an interactive response technology (IRT). The randomization number generated should be entered into the eCRF. Further details will be provided in the Pharmacy Manual.

#### 9.3.2 Blinding

This is a double-blind study. Tablets will be provided, pre-dispensed in blinded study kits. All tablets will be identical in appearance and size.

According to the randomization schedule as indicated in the Schedule of Assessments ([Table 1](#)) and in accordance with the Pharmacy Manual, the Investigator or designee will obtain the kit

number from the IRT for the patient and the kit number will be provided to the blinded pharmacist or designee at the study center who is responsible for the preparation of study drug. The blinded pharmacist will then dispense the correct kit number to the patient.

Each patient will receive 2 kits: the first for Days 1 to 7 and the second for Days 8 to 14. The kits numbers should be recorded in the eCRF and in the pharmacy dispensing logs.

If an Investigator becomes unblinded to a given patient's study treatment that patient will be discontinued from the study unless there are ethical reasons for that patient not to be discontinued; approval from the Sponsor's medical monitor must be obtained in such instances.

In the event that emergency unblinding is required for a given patient because of AEs or concerns for the patient's safety or wellbeing, the Investigator may break the randomization code for the patient via the IRT, by which system the unblinding will be captured. The Investigator is responsible for notifying the medical monitor and/or Sponsor of such an event as soon as possible. The unblinding and its cause will also be documented in the eCRF.

#### **9.4 Dosage Modification**

No dose modification is permitted during this study.

#### **9.5 Treatment Accountability and Compliance**

The pharmacist or other designated individual will maintain records of study treatment delivered to the study site, the inventory at the study site, the distribution to and use by each patient and the return of any required materials to the Sponsor. Study sites will be responsible for disposal of study treatment. Records should include dates, quantities, batch/serial numbers, expiration dates, in-clinic temperature log, and unique code numbers assigned to the product and study patients.

At each visit after initiation of treatment, study site personnel will record compliance of the patient with the patient's assigned regimen. Patients will be instructed to bring their diaries and unused/partially used/empty bottles back for inspection at each study visit. Patients are to be reminded of the importance of compliance with their assigned regimen, with an emphasis on taking their study drug on schedule and maintaining the prescribed interval between doses.

Investigators will maintain records that adequately document that the patients were provided with the correct study treatment kits and reconcile the products received from the drug dispensing center. Investigational product will not be disposed until accountability has been fully monitored.

Medication containers must be returned at each visit, as compliance will be assessed by tablet counts. Noncompliance is defined as taking less than < 80% or more than 120% of study drug during any outpatient evaluation period (visit to visit). Discontinuation for noncompliance is at the Investigator's discretion and is to be noted on the eCRF.

